1.4 Rationale

Prostate cancer is the leading cause of non-skin cancer in the United States, with an estimated 241,740 new cases diagnosed in 2012.¹² It is the number two cause of prostate cancer mortality among men in the US, accounting for 28,170 deaths.¹² The majority of these deaths are attributed to metastatic prostate cancer that is resistant to castration. Castration, defined as a serum testosterone level < 50 ng/dL, has been the mainstay of intervention for metastatic prostate cancer for decades. Castrate-levels of testosterone are achieved surgically through bilateral orchiectomy, or alternatively through treatment with administration of GnRH agonists or antagonists. Castrate-resistant prostate cancer (CRPC) often continues to rely on signaling through the androgen receptor that can be maintained even at very low (castrate) levels of circulating androgens. The androgen receptor signaling inhibitor enzalutamide has demonstrated activity against prostate cancer cells that overexpress the androgen receptor and are resistant to earlier generation anti-androgens such as bicalutamide.^{13,14} Enzalutamide is well-tolerated and is FDA-approved for use in combination with castration therapy for the

treatment of patients with metastatic CRPC who have experienced disease progression despite docetaxel chemotherapy.¹¹

Several predictors enable us to identify patients with localized prostate cancer who are at highest risk to develop metastatic CRPC. These include serum prostate specific antigen (PSA), Gleason score, and clinical tumor (T) stage on physical examination. Patients with high-risk localized, or locally advanced (those with radiographic or biopsy-demonstrated evidence of pelvic lymph node involvement) prostate cancer are routinely treated with a combination of GnRH agonist, first-generation anti-androgen, and EBRT. Androgen deprivation therapy (ADT) combined with radiation therapy has demonstrated superior survival outcomes when compared to either ADT or EBRT alone.¹⁻⁹ Standard of care treatment of men with high-risk localized or locally-advanced prostate cancer who receive external beam radiation therapy is 2-3 years of androgen deprivation therapy with a GnRH agonist, with concurrent treatment with a first-generation anti-androgen for the initial 4-6 months. EORTC 22961 demonstrated an improvement in 5 year overall survival for men with locally advanced prostate cancer treated with EBRT plus 6 months of GnRH agonist therapy plus a first-generation anti-androgen, followed by 30 months of GnRH agonist treatment alone, compared to this treatment without the additional 30 months of GnRH agonist therapy.² However, since many of these high-risk patients will go on to develop metastatic prostate cancer, there remains a significant need to improve upon the current treatment. No trial to date has tested the combination of enzalutamide with GnRH agonist therapy and external beam radiation therapy (EBRT) for patients with high-risk localized or locally-advanced prostate cancer. We hypothesize that this combination will be safe and well-tolerated. Once the safety profile has been established, we hypothesize that this combination may provide superior androgen signaling suppression and prostate cancer cell cytotoxicity compared to a first-generation anti-androgen plus GnRH agonist and improve clinical outcomes.

This pilot study will assess the safety and tolerability of combining enzalutamide with GnRH agonist treatment and EBRT. We hypothesize that administration of enzalutamide plus a GnRH agonist for 6 months in combination with EBRT, followed by treatment with a GnRH agonist alone for 18 - 30 months, will be a safe and well-tolerated treatment for patients with high-risk localized or locally advanced prostate cancer. We will perform correlative imaging and tumor tissue biopsy analysis to assess the radiographic response to enzalutamide plus GnRH therapy as well as intratumoral androgen signaling.

The primary endpoint is to determine the safety and tolerability of combining enzlutamide plus a GnRH agonist with EBRT up to 12 months following initiation of treatment with enzalutamide plus GnRH agonist. Primary endpoint measures are frequency of AEs with monitoring for

 Expected toxicities specific to the combination of enzalutamide plus GnRH agonist based on the clinical experience with this FDA-approved combination for the treatment of metastatic castration-resistant prostate cancer as annotated in section 1.2.2
 Expected radiation-related toxicities as annotated in section 4.4.1.8
 Unexpected severe AEs due to combination of enzalutamide plus GnRH agonist with EBRT.

Secondary endpoints will include

- 1. Molecular markers of androgen signaling and cell proliferation in prostate biopsy samples
 - a. Inhibition of androgen-regulated gene expression (potential targets to include NDRG1, FKBP5, TMPRSS2, and PSA) by qRT-PCR
 - b. Inhibition of androgen receptor (AR) nuclear localization and prostate cancer cell proliferation measured by immunohistochemistry (IHC)
 - c. Androgen metabolism in prostate biopsy samples

- 2. Serum PSA and testosterone following combination therapy with enzalutamide plus GnRH agonist therapy prior to initiation of radiation therapy
- 3. Changes in prostate tumor volume and activity following 2 months of combined enzalutamide plus GnRH therapy compared to baseline as measured by multi-parametric magnetic resonance imaging (MRI)

These results will lay the groundwork for subsequent randomized trials to compare this treatment combination with the current standard of care in patients with high-risk localized and locally-advanced prostate cancer.

1.5 Correlative Studies

In pre-clinical studies, enzalutamide was shown to inhibit androgen receptor signaling through multiple mechanisms.^{13,14} Enzalutamide inhibits androgen-induced receptor activation (binding of androgens to ARs in the cytosol), inhibits nuclear translocation of activated ARs, and inhibits the association of the activated AR with chromatin, even in the setting of AR overexpression and in prostate cancer cells resistant to anti-androgens such as bicalutamide. However, inhibition of AR signaling by enzalutamide has not been reported directly in primary patient tumor samples. We hypothesize that enzalutamide will impair AR nuclear localization and expression of AR-regulated genes in human tumors when administered in combination with GnRH agonist treatment. We hypothesize that this treatment combination will also result in a measurable anti-tumor response by muliparametric magnetic resonance imaging (MRI).

To test these hypotheses, we will obtain prostate cancer tumor biopsies at the time of study enrollment and following two months of treatment with enzalutamide plus GnRH agonist. MRI of the pelvis, protocolled to assess the prostate, will be performed prior to the initial biopsy and again prior to the subsequent biopsies obtained following two months of treatment.

2.0 STUDY OBJECTIVES

2.1 Primary Objectives

2.1.1 To determine the safety and tolerability of combining enzalutamide 160 mg by mouth daily with a GnRH and EBRT. Enzalutamide and GnRH agonist will be administered in combination for 6 months, beginning two months prior to the start of EBRT. Enzalutamide and GnRH agonist treatment will continue for the duration of EBRT and for approximately two months after completion of EBRT, for a total of 6 months of combined enzalutamide plus GnRH treatment. Patients will subsequently receive an additional 18 - 30 months of GnRH agonist therapy for a total of two - three years of GnRH agonist treatment. Safety and tolerability will be assessed by frequency and severity of adverse events with monthly monitoring for 12 months following initiation of enzalutamide plus GnRH therapy.

Secondary Objectives

2.1.2 To determine whether enzalutamide combined with GnRH agonist treatment inhibits intra-tumoral androgen-regulated gene expression (potential targets to include NDRG1, FKBP5, TMPRSS2, and PSA) as measured by qRT-PCR

- 2.1.3 To determine whether enzalutamide combined with GnRH agonist treatment impairs androgen receptor nuclear localization and cancer cell proliferation in targeted prostate cancer biopsy samples.
- 2.1.4 To determine the impact of enzalutamide combined with GnRH agonist on androgen metabolism in prostate biopsy samples.
- 2.1.5 To determine the impact of enzalutamide plus GnRH agonist therapy on serum prostate specific antigen (PSA) and testosterone following two months of treatment.
- 2.1.6 To describe any preliminary evidence of anti-tumor activity by assessment of objective response as determined by multiparametric MRI in patients with high-risk localized or locally-advanced prostate cancer.

2.2 Exploratory Objectives

Exploratory objectives are those defined above as secondary objectives 2.1.2 – 2.1.4.

2.3 Endpoints

2.1.1 Safety and tolerability will be assessed based on the rate of drug-related grade 1-5 adverse events experienced within the first 12 months of study treatment. These will be assessed via NCI's CTCAE v4.0 toxicity criteria.

2.1.2 Molecular markers of androgen-regulated gene expression in tumor biopsy samples will be assessed by qRT-PCR at the time of study initiation and following two months of combined treatment with enzalutamide plus GnRH agonist.

2.1.3 Androgen receptor nuclear localization and cancer cell proliferation (using Ki-67) will be analyzed by immunohistochemical analysis of tumor biopsy samples at the time of study initiation and following two months of combined treatment with enzalutamide plus GnRH agonist.

2.1.4 Enzymes of androgen metabolism will be assessed from prostate tumor biopsy specimens by qRT-PCR

2.1.5 Serum levels of prostate specific antigen (PSA) and testosterone will be measured at study initiation and following two months of treatment with enzalutamide combined with GnRH agonist.

2.1.6 Changes in prostate tumor volume and tumor activity will be measured by magnetic resonance imaging (MRI) at the time of study initiation prior to the initial study biopsy and again following two months of combined enzalutamide plus GnRH agonist treatment just prior to the second study biopsy to be performed at the time of fiducial marker placement.

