7.7 Stopping Rules

Based on experience from a completed phase III study, enzatlutamide is generally well tolerated when given in combination with a GnRH agonist. The most prominent safety concerns are primarily related to the risk of seizures. No completed study has examined the combination of enzalutamide with a GnRH agonist and concurrent radiation. The general tolerability of this combination is anticipated to be similar to that of radiation with concurrent GnRH agonist therapy. However, the absence of unexpected adverse events must be verified and is the primary endpoint of this study. Adverse events will be measured by NCI CTCAE criteria and will be monitored and recorded for a period of 12 months from initiation of the combination of enzalutamide plus GnRH agonist. Enrollment in the trial will be halted if unacceptable levels of toxicity are found as defined by 3 or more patients withdrawing from the study due to AEs.

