10.2 Sample Size and Accrual

We propose to enroll ten subjects in this pilot study. The expected accrual rate is 7 subjects over approximately 4 months. The primary endpoint is safety and tolerability of enzalutamide when combined with GnRH agonist and radiation therapy. Descriptive statistics will be computed to assess safety and tolerability. The highest AE score for each category over the 12 month period following initiation of treatment with enzalutamide plus GnRH agonist will be reported for each study subject in the summary statistics. Secondary endpoints assess mechanisms of enzalutamide plus GnRH action on prostate cancer tissue and quantitative imaging of localized prostate cancer response to enzalutamide plus GnRH therapy. As this is a pilot study, statistics will be used to report outcomes.

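### Section 2.3 limits the primary safety endpoint to drug-related AEs, while 1.4, 2.1.1, 10.2 and 10.3 count AEs without that limit, and nothing says which text prevails

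*Combined protocol and SAP*

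**What the plan says.** The primary endpoint is stated in several places.

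- Section 2.3 (Endpoints) uses "the rate of drug-related grade 1-5 adverse events experienced within the first 12 months of study treatment", graded by CTCAE v4.0.
- Section 1.4 (Rationale) gives AE frequency as the primary measure and lists what it covers. The list includes "Expected radiation-related toxicities as annotated in section 4.4.1.8" and "Unexpected severe AEs due to combination of enzalutamide plus GnRH agonist with EBRT".
- Section 2.1.1 (primary objective): "Safety and tolerability will be assessed by frequency and severity of adverse events with monthly monitoring for 12 months".
- Section 10.2 reports, for each subject, "The highest AE score for each category over the 12 month period following initiation of treatment".
- Section 10.3 plans descriptive statistics on how many AEs occur, and of what kind, in all patients over 12 months.
- Section 7.7 (Stopping Rules) says that "the absence of unexpected adverse events must be verified and is the primary endpoint of this study". It then says that AEs "will be monitored and recorded for a period of 12 months from initiation of the combination of enzalutamide plus GnRH agonist", without restricting which ones.

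On causality, 7.4 sets out steps for deciding on expedited reporting. It relates an event to the protocol therapy or study treatment on a scale running from definite to unrelated. Section 7.5 asks for causality with respect to the study drug in SAE reports. Section 4.4.1 describes radiotherapy as standard of care, yet it sits within the Treatment Plan. No section says whether it is part of study treatment.

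**The concern.** Section 2.3 is the section headed Endpoints, so an author could follow it and report drug-related events only. Another could follow 10.3 and report everything. Both could claim to have kept to the protocol, and the choice could be made after seeing the data.

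The two readings differ most on radiation toxicity. The stated question is whether adding enzalutamide and a GnRH agonist to EBRT is safe. If the combination worsened bowel or bladder effects, those events could well be recorded as radiation toxicity, and a drug-specific filter would remove them from the primary rate. The protocol's own lists show how hard the call is: diarrhea and hematuria appear both as enzalutamide effects in 8.1 and as radiation effects in 4.4.1.8. In one open-label arm, assigning such an event to drug or radiation is a matter of judgement.

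**Working it through.** The documents give no alpha, power, target rate or sample-size formula, so there is no figure to reproduce. The check compares the texts and then follows one event through them.

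**1. Which AEs each text counts**

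| Section | AE set | Radiation toxicity |
|---|---|---|
| 2.3 | drug-related, grades 1-5 | out, if read as drug-specific |
| 1.4 | AE frequency, with listed components | in, by name |
| 2.1.1, 10.2, 10.3 | AEs, no filter | in, through 7.3.1 |
| 7.7 | unexpected AEs | not settled |

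Only 1.4 names radiation toxicity. For 2.1.1, 10.2 and 10.3 the inclusion follows from 7.3.1, which defines an AE whether or not treatment caused it.

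**2. Whether the 2.3 filter can be applied**

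Section 7.4 attributes to protocol therapy or study treatment as a whole. It does not separate enzalutamide, GnRH agonist and EBRT. Its reference to the agent(s) concerns the reporting of events more than 30 days after the last dose. The drug-causality item in 7.5 belongs to SAE reports. None of these gives a drug-versus-radiation attribution for ordinary grade 1-5 AEs.

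**3. One event: proctitis attributed to EBRT alone, the patient's only bowel event**

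- 1.4, 2.1.1, 10.2, 10.3: it counts.
- 2.3, with drug meaning enzalutamide (8.2.1 equates study drug with enzalutamide): it does not count.
- 2.3, using 7.4 attribution with EBRT as part of study treatment: it counts.
- 7.7: undetermined. Section 1.4 treats the toxicities in 4.4.1.8 as expected. Step 4 of 7.4 tests expectedness, for expedited reporting only, against agent listings, and proctitis is not among the enzalutamide effects listed in 8.1.

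**4. Size**

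Let k be the number of patients whose only event in a category is attributed to EBRT alone. The shift in that category's proportion is k/n. The study summary gives n = 7, while 10.2 says "We propose to enroll ten subjects in this pilot study".

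- n = 7: 1/7 = 0.143, or 14.3 points per patient.
- n = 10: 1/10 = 0.100, or 10.0 points per patient.

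The documents give no EBRT toxicity rate, so k is unknown and may be zero. The disagreement over n is a separate matter.

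**The case against.** The strongest reply is that 10.3 is the operative analysis text. It restates the primary endpoint and gives an unfiltered analysis. Sections 1.4, 2.1.1 and 10.2 agree with it. Section 6.2 analyses everyone who took at least one dose, and 7.2 follows AEs whatever their relationship to study drug. On this view 2.3 is a lone outlier, and a drug-related table is only a subset of what 10.3 produces. This shows which way to reconcile the texts. It does not show that they agree: 2.3 is the designated endpoint section and nothing ranks it below 10.3.

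Four stronger readings are tempting but not supported.

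- *Three rival endpoint definitions of equal standing.* The 7.7 sentence is part of the rationale for a stopping rule, overlaps a component of 1.4, and is followed by unfiltered AE recording. It needs aligning, but it is not a third endpoint on a par with the others.
- *Drug attribution is absent, or each AE is rated only once.* Section 7.4 is a reporting procedure and says nothing about the number of ratings. Section 7.5 does ask for drug causality for SAEs. The case report form is not among the documents, so separate attribution could exist there.
- *EBRT proctitis is certainly excluded under 7.7.* Step 3 above shows that this is unsettled.
- *A measurable bias.* Any range for k would be pure assumption.

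**Conclusion.** The inconsistency is real: the primary numerator differs between 2.3 and the sections that apply no relatedness filter, and no rule of precedence resolves it. The direction is conditional. If 2.3 is applied as a drug-specific filter, EBRT-only events drop out and the primary rate can only fall. If relatedness is judged under 7.4 and EBRT is part of study treatment, those events stay in and the shift is zero. Beyond the 1/n step per affected patient, the documents do not allow the size to be estimated.

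A reader might infer that patient protection or an error rate is at risk. It is not. The study is descriptive, with no test or power calculation. The halting rules in 7.7 and 10.1 count withdrawals due to AEs and, in 10.1, patients with SAEs, with no relatedness filter. What is at stake is what the primary result counts, which should be settled before the data are seen.

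**What to change.** - **2.3:** delete the drug-related restriction. Proposed definition: *all adverse events, regardless of attribution, over the 12 months from initiation of enzalutamide plus GnRH agonist, reported as the number and nature of AEs and the worst grade per category for each treated patient*. This matches 10.2 and 10.3.
- **7.7:** reword the endpoint sentence so that unexpected AEs are reported as part of the endpoint defined in 2.3.
- **7.4:** state whether EBRT is part of study treatment. Only then report related AEs, as a secondary subset, provided attribution is recorded for all AEs against that defined object. A subset specific to enzalutamide would need attribution recorded separately for enzalutamide, GnRH agonist and EBRT.

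The cost is wording changes in three sections and one additional table. AEs are already to be recorded for 12 months under 7.7, so the primary analysis needs no new data. A per-modality subset might need an extra case report form item, which cannot be judged from the documents. The reported AE frequency may look less favourable than a drug-related rate would.

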3.0 Subject ELIGIBILITY

Eligibility waivers are not permitted. Subjects must meet all of the inclusion and exclusion criteria to be registered to the study. Study treatment may not begin until a subject is registered.

3.1 Inclusion Criteria

3.1.1 Histologically proven adenocarcinoma of the prostate obtained within 6 months of screening. Patients in whom a diagnosis of high-risk localized or locally-advanced prostatic adenocarcinoma is suspected based on a serum PSA > 20

ng/mL or clinical T3 disease by digital rectal examination, but who have not yet undergone diagnostic prostate biopsy, will be eligible for screening and initial MRI and targeted prostate cancer biopsies which will be obtained at the same time as diagnostic biopsies. Those patients in whom the diagnostic biopsies confirm prostatic adenocarcinoma will be permitted to continue with study treatment if they meet all additional eligibility criteria.

- 3.1.2 Age \geq 18 years.
- 3.1.3 Eastern Cooperative Oncology Group (ECOG) performance status < 2
- 3.1.4 Adequate organ and marrow function as defined below:
 - leukocytes ≥ 3,000/mcL
 - absolute neutrophil count \geq 1,500/mcL
 - platelets ≥ 100,000/mcl
 - hemoglobin > 10 g/dL
 - total bilirubin \leq 1.5 X institutional upper limit of normal (except
 - for patients with documented Gilbert's disease)
 - AST(SGOT)/ALT(SPGT) ≤ 2.5 X institutional upper limit of normal
 creatinine ≤ 1.5 X institutional upper limit of normal or estimated glomerular filtration rate < 45 mL/min/1.73m2, given the risk of nephrogenic systemic fibrosis when using gadolinium-based intravenous contrast agents in these subjects.
 serum testosterone ≥ 100 ng/dL
- 3.1.5 Men who are sexually active with female partners of child-bearing potential must agree to use adequate contraception (hormonal or barrier method of birth control; abstinence) prior to study entry, for the duration of study participation, and for *90* days following completion of therapy. Should a woman become pregnant or suspect she is pregnant following intercourse with a study participant during his participation in this study, she should inform her treating physician immediately, and the study principal investigator should be informed immediately.
 - 3.1.6.1 A female of child-bearing potential is any woman (regardless of sexual orientation, having undergone a tubal ligation, or remaining celibate by choice) who meets the following criteria:
 - Has not undergone a hysterectomy or bilateral oophorectomy; or
 - Has not been naturally postmenopausal for at least 12 consecutive months (i.e., has had menses at any time in the preceding 12 consecutive months).
- 3.1.6 Patients must be candidates for long-term androgen deprivation in combination with EBRT for the treatment of high-risk or locally-advanced prostate cancer by the following criteria:
 - High risk disease: T3a or Gleason 8-10 or serum PSA > 20 ng/mL
 - Gleason 7 also allowed if > 50% of cores positive for cancer or PSA velocity > 2 ng/mL/year in preceding 12 months
 - Locally advanced (very high risk) disease: T3b-T4
- 3.1.7 Patients may have radiographic evidence of metastasis in regional lymph nodes (N1 disease as defined by the National Comprehensive Cancer Network Prostate Cancer Guideline Version 3.2012) at the discretion of the treating physicians, if regional lymph nodes can be included in the planned radiation field.

- 3.1.8 Participants in the study must permit targeted prostate biopsy prior to initiation of study treatment and at the time of fiducial marker placement
- 3.1.9 Able and willing to provide written authorization for use and release of health and research study information
- 3.1.10 Ability to understand and the willingness to sign a written informed consent.

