3.2 Exclusion Criteria

- 3.2.1 Prior treatment with the following agents known to have endocrine effects on prostate cancer: GnRH agonist, GnRH antagonist, anti-androgen (bicalutamide, nilutamide, flutamide), ketoconazole, diethylstilbestrol, estrogen, abiraterone acetate. Concurrent use of 5α -reductase inhibitors finasteride or dutasteride is permitted for patients who have been already receiving either of these treatments for at least 1 month at the time of study enrollment. Baseline PSA must have been obtained in such patients after at least 1 month on 5α -reductase treatment. Initiation of treatment with 5α -reductase inhibitors is not permitted within the first 12 months of study participation.
- 3.2.2 Concomitant treatment with agents thought to have endocrine effects on prostate cancer: PC-SPES, saw palmetto
- 3.2.3 Treatment with corticosteroids within 4 weeks prior to enrollment.
- 3.2.4 Treatment with androgens within 6 months prior to study enrollment.
- 3.2.5 Subjects may not be receiving any other investigational agents. Concurrent enrollment in another clinical investigational drug or device study is prohibited.
- 3.2.6 Prostate cancer metastases to the bones, viscera, or non-regional lymph nodes (lymph nodes other than pelvic lymph nodes within the radiation treatment field)
- 3.2.7 Serum PSA > 160 ng/dL
- 3.2.8 History of malignancy (other than non-melanoma skin cancer) within 5 years of enrollment
- 3.2.9 Patients with histologic evidence of small cell carcinoma of the prostate will not be eligible.
- 3.2.10 Treatment for malignancy with anticancer therapy, including cytotoxic agents, hormonal agents, or immunotherapy, within 5 years of enrollment
- 3.2.11 History of allergic reactions attributed to compounds of similar chemical or biologic composition to *enzalutamide* or other agents used in this study.
- 3.2.12 Uncontrolled intercurrent illness including, but not limited to, ongoing or active infection, symptomatic congestive heart failure (> NYHA class II hear failure), unstable angina pectoris, cardiac arrhythmia, chronic active hepatitis, acute hepatitis, uncontrolled diabetes mellitus, or psychiatric illness/social situations that would limit compliance with study requirements.
- 3.2.13 Patients with any of the following within 6 months of enrollment: deep vein thrombosis, pulmonary embolus, myocardial infarction, cerebrovascular accident, unexplained loss of consciousness.

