6.1.2.2 Image acquisition

Patients will undergo an MR examination with our routine clinical protocol using a 3T MRI system (Philips Medical Systems, Cleveland, OH) and a pelvic phasedarray coil. Endorectal coil will not be used. The patient is imaged in the supine position and artifacts due to bowel peristalsis are minimized with sublingual administration of 0.250 mg of hyoscyamine sulfate (Levsin). Our protocol includes T2-weighted fast spin-echo images in the transverse, sagittal, and coronal planes; axial diffusion-weighted transverse single shot echo planar image (with ADC map); T1-weighted gradient-echo images acquired before, during, and following the intravenous injection of a single dose of a gadolinium-based contrast as it is done for our clinical prostate MRI protocol. Additional pulse sequences such as arterial spin labeling (ASL), blood oxygen level dependent (BOLD), and others might be incorporated into the MRI protocol for additional research purposes; the total examination time will not exceed 1.5 hours and the amount of intravenous contrast administered will be similar to the dose given for clinical prostate MRI examinations. If at any point during the study the participant indicates a desire to withdraw, the exam will be interrupted.

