6.1.2.3 Potential risks associated with MRI

Patients will be screened for MRI contraindications and these will be exclusion criteria for this study. Safety rules will be strictly enforced and followed by the research study team, MRI technologists, and the study subjects themselves. During the MRI scanning process, the study team is in constant two-way communication with the participant and can remove him from the magnet immediately as needed. The MRI personnel are trained to respond to emergency situations, further supported by an institutional Rapid Response Team should an adverse event arise during the study visit. Standard radiofrequency coils provided by manufacturers of MRI machines will be used in this study. The risks associated with the use of these coils are minimal. However, with any RF coil, there is a small risk of skin burns if the coil is used improperly or is malfunctioning. The MRI staff at UT Southwestern Medical Center is fully trained in the proper use of these devices.

Subjects will be screened for renal impairment prior to administration of gadolinium-based contrast agents as it is routinely done in the Radiology Department at UT Southwestern. A serum creatinine determination within 30 days prior to the research MRI examination must be available to calculate an estimated glomerular filtration rate (eGFR). An eGFR calculation may be repeated closer to the MRI appointment if the patient's medical condition has changed. An eGFR ≥45 mL/min/1.73m2 is considered acceptable for administration of a standard weight-based dose of intravenous contrast for research purposes.¹⁷

We do not anticipate significant psychological stress related to this study procedure. Patients will be able to refuse to answer any of the questions, take a break or stop their participation in this study at any time.

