6.1.2.6 Evaluation of changes in tumor volume and tumor activity

Tumor volume will be assessed using a planimetric approach.²¹ On each MRI prostate section the outline of suspicious areas will be traced on the computer screen and the surface area will be calculated. After counting the number of separate foci and defining the most representative site of origin, tumor foci volume will be calculated by multiplying the sum of the suspicious surface areas by the slice thickness (usually 2-3 mm).

Tumor activity will be assessed using apparent diffusion coefficient (ADC) derived from diffusion-weighted imaging, which has been shown to correlate with Gleason score and percentage of tumor on core biopsy (as surrogates for tumor aggressiveness).^{22,23} ADC values will be derived by drawing a region of interest on the confirmed tumors, and expressed as mean values and histograms.

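### Two eligibility limits are wrong as written: 3.1.4 counts an eGFR below 45 as adequate renal function, and 3.2.7 excludes PSA above 160 ng/dL, which is 1.6 ng/mL

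*Combined protocol and SAP*

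**What the plan says.** **Renal function.** Section 3.1.4 is a list of what counts as adequate organ and marrow function, so meeting a line qualifies the patient. Its renal line accepts creatinine up to 1.5 × ULN or, as an alternative, "estimated glomerular filtration rate < 45 mL/min/1.73m2, given the risk of nephrogenic systemic fibrosis" with gadolinium contrast. Section 6.1.2.3 sets the rule for the scan itself: "An eGFR ≥45 mL/min/1.73m2 is considered acceptable for administration of a standard weight-based dose of intravenous contrast". It adds a timing requirement: "A serum creatinine determination within 30 days prior to the research MRI examination must be available". Contrast is part of the protocol MRI, since section 6.1.2.2 includes "T1-weighted gradient-echo images acquired before, during, and following the intravenous injection of a single dose of a gadolinium-based contrast".

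**PSA.** Section 3.2.7 excludes "Serum PSA > 160 ng/dL". Section 3.1.6 defines one route into the trial as "High risk disease: T3a or Gleason 8-10 or serum PSA > 20 ng/mL". Section 3.1.1 also lets men without a diagnostic biopsy be screened on PSA above 20 ng/mL. They have the MRI and biopsies, and if cancer is confirmed they "will be permitted to continue with study treatment if they meet all additional eligibility criteria".

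**Discretion.** Section 3.0 rules out waivers and requires every criterion to be met before registration.

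**The concern.** Eligibility limits are decision rules, and with waivers barred the site must apply them as printed. Both limits, applied that way, do the opposite of what the rest of the protocol needs.

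The renal line makes a low eGFR a way to qualify. A man with creatinine 2.0 × ULN passes at eGFR 30 and fails at eGFR 60. At stake is the registration of men who then cannot have the contrast series.

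The PSA line closes the PSA route that 3.1.1 and 3.1.6 open. At stake is a main part of the target population. That includes unbiopsied men who would undergo research MRI and biopsy and then have to be turned away by 3.2.7. If staff instead enrol them on the presumed meaning, those men are ineligible on paper.

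**Working it through.** No sample-size or power figure is involved. The check is a comparison of rules and a unit conversion.

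**Renal rule.** Let C be creatinine as a multiple of ULN and E be eGFR in mL/min/1.73m². Compare three rules:

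- Written (3.1.4): C ≤ 1.5 or E < 45
- Both required (consistent with 6.1.2.3): C ≤ 1.5 and E ≥ 45
- Sign changed only: C ≤ 1.5 or E ≥ 45

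| C | E | Written | Both required | Sign changed only |
|---|---|---|---|---|
| ≤ 1.5 | ≥ 45 | pass | pass | pass |
| ≤ 1.5 | < 45 | pass | fail | pass |
| > 1.5 | < 45 | pass | fail | fail |
| > 1.5 | ≥ 45 | fail | fail | pass |

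The written rule differs from the both-required rule in 2 of 4 cells, the two with E < 45. It differs from the sign-only rule in 2 of 4 cells, the two with C > 1.5. The sign-only rule still admits men with acceptable creatinine and E < 45, so changing the sign alone does not meet the gadolinium reason given in the line. These are logical combinations, not patient frequencies, which the documents do not give.

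**PSA rule.** 1 dL = 100 mL, so ng/mL = ng/dL ÷ 100.

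- Exclusion limit (3.2.7): 160 ÷ 100 = 1.6 ng/mL.
- Inclusion threshold (3.1.1 and 3.1.6): 20 ng/mL × 100 = 2,000 ng/dL.
- Ratio of inclusion threshold to exclusion limit: 20 ÷ 1.6 = 12.5.
- Window for a man who qualifies on PSA: above 20 and at most 1.6 ng/mL, which is empty.
- T-stage and Gleason routes: open only at PSA ≤ 1.6 ng/mL.
- Gleason 7 velocity route (more than 2 ng/mL/year over the preceding 12 months): closed as well if the rise is measured over the full year, because PSA must then exceed 2 ng/mL.
- If 160 ng/mL was meant (assumption): 160 × 100 = 16,000 ng/dL, and 16,000 ÷ 160 = 100, so the printed limit is 100-fold too low. The PSA route would then run from above 20 up to 160 ng/mL.

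**Same slip elsewhere.** Section 5.1.12.2 gives 20 ng/dL (20 ÷ 100 = 0.2 ng/mL) while citing 3.1.1, which has ng/mL. Section 3.1.1 governs, so this one is minor.

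**Consequence for the MRI endpoint.** A man without contrast loses the dynamic series. Volume is planimetric, and for activity 6.1.2.6 states: "Tumor activity will be assessed using apparent diffusion coefficient (ADC) derived from diffusion-weighted imaging". Both remain obtainable. However, 6.1.2.4 uses the dynamic series as one way to identify suspicious areas, so the volume tracing would lose one input. One such man is 1/7 = 14% of the study at the summary's size of 7, or 1/10 = 10% at the ten given in section 10.2.

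**The case against.** The strongest reply is that the intended meaning is plain and the harm is contained. The renal line states its own reason, and 6.1.2.3 carries the working rule with a recent creatinine. What remains is possible loss of the contrast series for a secondary, descriptive endpoint; the primary endpoint, adverse events, needs no contrast. The PSA contradiction would surface with the first PSA-qualified man and cannot silently bias a result. This is right about contrast exposure and about bias. It does not remove the need to amend, because a no-waiver clause leaves no route for applying a presumed meaning.

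Three narrower points have some force.

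- eGFR is calculated from creatinine, so the cells do not cross freely. High creatinine with eGFR of 45 or above may be rare or absent, and the eGFR 60 example shows the rule's logic rather than a known patient. The two cells with eGFR below 45 do not depend on it.
- The documents do not settle whether the baseline contrast check precedes registration. Section 5.4 puts the MRI in the pre-study window, while 5.1.12.1 places it at enrolment. The repeat MRI in weeks 7–11 (5.2.3) comes after registration on either reading.
- Requiring both renal conditions goes further than reversing a sign, and the investigators could instead allow a non-contrast MRI. That is a legitimate design choice, but it would have to be written in. As the protocol stands, contrast is part of the scan and the line's reason is contrast safety.

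**Conclusion.** Both limits are wrong as written and must be corrected. The renal line admits the eGFR range that 6.1.2.3 does not accept for contrast, and it misclassifies 2 of the 4 creatinine/eGFR combinations under either plausible intention. The PSA line shuts out every man who qualifies on PSA above 20 ng/mL and leaves the stage and Gleason routes open only at 1.6 ng/mL or below.

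The PSA contradiction rests on unit conversion alone. That 160 ng/mL was intended is an inference from the units in 3.1.1 and 3.1.6. That both renal conditions should apply follows from the gadolinium reason and 6.1.2.3. How many men would be affected cannot be derived from the documents.

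A minor inconsistency sits alongside. Section 7.1.2 makes predisposing seizure risk factors disqualifying, but 3.2.14 covers only a history of seizure or seizure disorder, and 3.2.13 and 3.2.15 fill the gap only in part. Section 4.3 lists seven threshold-lowering drug classes without a rule, and 3.2.18 names none of them. Part of section 7.1 was not available to me, so I give the drug list no weight.

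**What to change.** - **3.1.4:** require creatinine ≤ 1.5 × ULN **and** eGFR ≥ 45 mL/min/1.73m². Do not simply reverse the sign and keep the alternative.
- **3.2.7:** state the limit in ng/mL, presumably above 160 ng/mL, with the investigator to confirm the figure.
- **5.1.12.2:** change ng/dL to ng/mL.
- **Minor alignment:** carry the 7.1.2 risk-factor rule into 3.2.14, and state whether the drugs listed in 4.3 are prohibited, allowed with caution or need a washout, unless this is already covered elsewhere in 7.1.
- **Patients already screened, if any:** re-check them against the corrected renal and PSA limits.

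The cost is a short amendment to the eligibility text and checklist. Men with eGFR below 45 would be screened out before registration, instead of possibly being found unfit for contrast afterwards.
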